The combination of elaborate marketing campaigns in social media and the research app will allow for a very efficient recruitment, eligibility check and data collection. Those being interested will register online after confirming inclusion criteria: 1) between the ages of 16-19, 2) have previously sought professional help for anxiety and/or depressive symptoms, 3) have been feeling fine or mostly fine for the last two months. Before further assessment and trial inclusion, the adolescent will sign informed consent digitally. After consent is obtained, they will be invited to download the research app. To ensure eligibility, preassessment with the digitalized self-report format of the clinical interview Composite International Diagnostic Interview 5th revision (CIDI 5.0 (31)) will be conducted to make sure that the adolescent have had a previous episode of depression and/or an anxiety fulfilling the DSM-5 criteria, and no current ongoing episode or ongoing anxiety disorder before trial entry and randomization are conducted.

Table 1. Participant eligibility

Inclusion criteria

 • Currently in full or partial remission for a minimum of 2 months from a depressive disorder or an anxiety disorder. • Age between 16-19. • Native or fluent Norwegian or Scandinavian language skills. • Willingness to take part even when allocated to the non-preferred intervention.
Exclusion criteria

 • Ongoing depressive disorder, ongoing anxiety disorder. • Recent (within ~1 year) completion of the “Tankevirus”-intervention. • No available smartphone.

PRIMARY ENDPOINT: The primary endpoint will be time until relapse and number of relapses to depression during the 12-months follow-up post-randomization. To assess relapse, the app will give notifications for biweekly assessments with the ultra-brief PHQ-4 (32) assessing both anxiety and depressive symptoms. If the depression subscale indicates relapse (score ≥ 3), the remaining questions from PHQ-A (33), that is the adolescent version of PHQ-9 (34), will pop-up. The items in PHQ-9 aligns with the diagnostic criteria for major depressive disorder as described in the Diagnostic and

Statistical Manual of Mental Disorders (35) and an algorithm can therefore indicate depressive relapse (36). This procedure of biweekly assessments will also provide a precise measure of time to relapse.

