participants. Our pre-inclusion assessments and inclusion criteria will be less comprehensive, allowing for more participants to be included. Presuming that the three birth cohorts in Norway comprises 150.000 adolescents aged 16-19. Of these, 5 % will currently have an anxiety disorder and 2% will have a depressive disorder as per diagnosis in specialized health care (45), amounting to approximately 10.500 potential participants. We would then need to recruit 4.7 % of this population (495/10.500) to complete this study. When considering that we require the adolescents who are in remission only, that they may have fulfilled the criteria at earlier ages, and that only a minority of adolescents are diagnosed and/or treated in specialized health care even when having profound symptom load (46), these numbers are conservative.

Attrition is another risk factor. The evidence in relation to decentralized trials and retention among adolescents is still scarce, and recommendations currently rely on the use of well-evidenced strategies (e.g., incentives, reducing barriers and burden, and investing in building positive relationships with participants) when engaging adolescents in longitudinal health studies (47). Hence, the adolescents will be issued a universal gift card worth 1200 NOK when they have completed their participation. Each assessment will be initiated by a prompt about how much it's pays to promote its completion. The therapists in the therapist-led interventional arm have extensive experience delivering these interventions to youths and are good at building positive relations. Due to the digitalized format, push notification will be used to promote engagement.

ETHICS: There is an inherent risk of relapse among these adolescents, and it will therefore be important to detect if their state deteriorates during the trial and offer them advice on how they can proceed to receive the adequate level of care. The contact information to the project group will always be available in the app. At all follow-ups, if a certain symptom load is detected, a pop-up message will appear, including our contact information and information about treatment providers. If CIDI 5.0 pre-assessment reveals an ongoing disorder, the adolescent will be advised on whom to contact for receiving adequate level of care and will not be included in this trial.

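### The sum-score gate in front of the relapse algorithm does not nest with it: under conventional scoring, two core-symptom patterns are screened out at that assessment, so some relapses are missed or recorded late

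*Protocol*

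**What the plan says.** All of this is in Protocol section 1.3 unless noted.

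- **Endpoint.** "The primary endpoint will be time until relapse and number of relapses to depression during the 12-months follow-up post-randomization".
- **Screen.** For relapse, "the app will give notifications for biweekly assessments with the ultra-brief PHQ-4 (32) assessing both anxiety and depressive symptoms".
- **Gate.** "If the depression subscale indicates relapse (score ≥ 3), the remaining questions from PHQ-A" are shown; below that score they are not.
- **Decision rule.** "The items in PHQ-9 aligns with the diagnostic criteria for major depressive disorder", and on that ground the protocol says an algorithm can indicate a depressive relapse. It cites a reference for this and prints neither the item scoring nor the item cut-off.
- **Other measurements.** The 3-, 6- and 12-month assessments (SECONDARY OUTCOMES and ASSESSMENTS) cover repetitive negative thinking, somatic complaints, well-being, quality of life and service use, with satisfaction at 3 months in the intervention arms. No ungated PHQ-A and no repeat of the CIDI is listed.

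**The concern.** The gate and the algorithm use the same two core items in different ways. The gate adds them. A rule built on the diagnostic criteria asks whether at least one of them is present and then counts symptoms. A sum rule placed in front of an either/or rule can turn away people whom the second rule would classify as positive. Whether it does so here depends on the level at which a core symptom counts.

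Both components of the primary endpoint pass through this gate, and the protocol describes no other way for a relapse to be recorded. The seven items behind the gate are not collected when it stays shut, so no analysis plan can recover them. The rule therefore has to be settled in the protocol and the app. At stake are the number of relapses counted and the accuracy of the relapse date, which the protocol presents as a strength of biweekly assessment.

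**Working it through.** **Inputs from the protocol.** The gate is a sum of the two depression items of at least 3. The algorithm works on the PHQ-9 items and is aligned with the criteria for major depressive disorder.

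**Assumptions, not printed in the protocol.** Each item scores 0-3. A symptom is present at 2 or more, except the suicidality item at 1 or more. The algorithm needs at least five symptoms, at least one of them core. The core cut-off c is varied over 1, 2 and 3.

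**Step 1: core pairs against the gate.** There are 4 × 4 = 16 pairs (a,b). A pair is core-positive if max(a,b) ≥ c; the gate opens if a + b ≥ 3, which holds for 10 of the 16.

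| Core cut-off c | Core-positive pairs | Blocked by the gate | Which |
|---|---|---|---|
| 1 | 15 | 5 | (0,1), (1,0), (1,1), (0,2), (2,0) |
| 2 | 12 | 2 | (0,2), (2,0) |
| 3 | 7 | 0 | none |

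At c = 2, the pairs (2,1) and (3,0) pass. Only one item at exactly 2 with the other at exactly 0 is stopped.

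**Step 2: can a blocked person meet the algorithm?** Yes. With one core symptom present, 5 − 1 = 4 of the other seven items must be positive. The lowest such total is 2 + 0 + (3 × 2) + 1 = 9, using the suicidality item at 1. The highest is 2 + 0 + (7 × 3) = 23. The blocked group is therefore not confined to low total scores.

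**Step 3: count of full nine-item patterns at c = 2.** The other seven items have 4^7 = 16,384 patterns. At least four are positive in 9,472 of these, and at least three in 13,632. Eight core-positive pairs have exactly one core item at 2 or more; four have both.

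- Algorithm-positive patterns: 8 × 9,472 + 4 × 13,632 = 75,776 + 54,528 = 130,304.
- Blocked by the gate: 2 × 9,472 = 18,944.
- Ratio: 18,944 / 130,304 = 14.5%.

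This treats every pattern as equally likely. It shows that the gap is not a single odd case, but it is not a prevalence and does not estimate the share of relapses lost.

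**Step 4: duration of the block.** It applies assessment by assessment. If a later screen sums to 3 or more, the remaining items open and the relapse can be recorded, at least one two-week cycle late. If the pattern persists or resolves first, the relapse is missed.

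**Step 5: effect of an either/or gate.** At c = 2, every pair with a sum of 3 or more already has an item at 2 or more. Opening the gate at max(a,b) ≥ 2 therefore takes it from 10 pairs to 12, adding (2,0) and (0,2) and removing none.

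**The case against.** **The decisive cut-off is not in the document.** This stands. The level of 2 is the usual PHQ-9 convention and enters here as an assumption; at a core cut-off of 3 the gate loses nobody. Leaving the cut-off to an analysis plan is acceptable and is not the complaint. The complaint is that the gate is fixed without being tied to that cut-off.

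**The gate is a deliberate limit on burden.** The protocol wants short scales to avoid fatigue and names attrition as a risk, and a two-stage screen trades away some sensitivity. That is fair as a general aim, but the change adds items for only two score patterns at a cut-off of 2.

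**The gate may simply be the definition.** The wording that a score of 3 or more indicates relapse, followed by an algorithm that indicates relapse, could be read as two definitions of the event. The order of the text reads more naturally as screen, further items, algorithm. If the gate itself were the definition, the nesting problem would disappear. One clarifying sentence settles it.

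Three stronger readings are tempting and not supported:

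- *Such participants can never be recorded as relapsed.* Screening repeats every two weeks for 12 months, so later capture remains possible.
- *The gap favours the interventions,* because treatment may lift mood more than interest. The protocol links repetitive negative thinking to negative mood but makes no comparison with interest, and the same gate applies in all three arms.
- *Deterioration goes unseen.* ETHICS says "it will therefore be important to detect if their state deteriorates during the trial". The PHQ-4 answers are still collected every two weeks, other outcomes are measured at 3, 6 and 12 months, and the symptom-load message at follow-ups is not tied to this gate. Only the remaining PHQ-A items are hidden.

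**Conclusion.** The point holds in a limited form. With items scored 0-3 and a core symptom counted at 2 or more, the gate and the algorithm do not nest: 2 of 12 core-positive pairs, (2,0) and (0,2), are blocked. The number blocked is 5 of 15 at a cut-off of 1 and 0 of 7 at a cut-off of 3. A blocked participant who also has at least four other positive symptoms is not recorded as relapsed at that assessment, and the relapse is missed or dated late.

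The firm consequence is reduced sensitivity and a less precise time to relapse, in every arm. The documents give no information on how common these patterns are, so neither the loss of events nor its effect on power can be put in figures. The finding does not call the stated sample sizes of 238 and 495 into question. The correction is worth making because it protects capture of the primary event at little cost and cannot be made after data collection.

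**What to change.** 1. Replace the sum-score gate by an either/or gate: show the remaining PHQ-A items when either depression item scores 2 or more, or whatever level the chosen algorithm uses for a core symptom. If that level is 3, the present gate already loses nobody and no change is needed.
2. State that relapse is the algorithm result, and that the gate only determines whether the remaining items are shown. Reword the phrase that treats a subscale score of 3 or more as itself indicating relapse.
3. Record the item cut-off alongside the gate, in the protocol or the analysis plan, so that the nesting can be checked.

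The cost is one branching rule in a research app that Protocol section 3.2 describes as still under development. The downside is that some participants see seven extra items at some assessments.

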cost-efficient manner. Still, however, none has systematically investigated if interventions aimed at relapse prevention require therapist-involvement to be effective. While alliance is a central common factor for the effect of all psychological treatment, this factor is lacking in unguided treatment regiments. Yet, in a small young adult depression prevention trial in an at-risk population, the effect sizes for guided and unguided self-help programs were similar (25), suggesting that engagement is important when investigating outcomes of digital interventions (26). If the therapist is redundant when delivering these programs, barriers for entering relapse prevention programs are reduced considerably.

Among adolescents who has experienced depressive episodes and/or anxiety disorders, the current project will adopt a multiarmed randomized design for assessing the efficacy of targeting transdiagnostic processes for relapse prevention at different level of clinician involvement. The main aim is to reduce number of relapses to depression and time to relapse over the course of twelve months. The project will also investigate the mediating effect of the hypothesized mechanism (i.e., RNT) on the subsequent relapse risk.

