INTERVENTIONS: “Tankevirus” is an award-winning psychological intervention developed for adolescents aged 16 and above, including a book, a mastery course, and a smartphone app. It is based on the principles of CBT to help individuals identify and challenge negative thought patterns that can lead to anxiety and depression. “Tankevirus” has been extensively evaluated. From 2017-2021, 50.000 students took part in the overarching “Tankevirus” School program, and 9 out of 10 thought the interventions were useful and would recommend it to a fellow student. The “Tankevirus” smartphone app is freely available, and within 16 months, it was downloaded by 26.000 adolescents. Based on patient reported outcome measures, 7 out of 10 reported improvements in overall health and increased quality of life. The app includes several components to increase engagement with the intervention material, which is a necessary prerequisite for digital mental health interventions to be effective (26), and smartphone apps which have elements built in to promote engagement are associated with larger effect sizes (29). In this project we will include two different formats of the “Tankevirus”-interventions, in addition to a control condition:

- **“Tankevirus” therapist-guided group intervention:** The intervention will be delivered by therapists having extensive experience with this age group in the form of 3 weekly 75-minutes sessions to groups of approximately 30-35 participants. An online GDPR-compliant webinar-platform including chat-options will be used (edumeet.org). Adolescents will remain anonymous to each other to decrease barriers to participation. The adolescents will book their preferred timeslot online. For the participants randomized to this intervention, a certain waiting period (~1 week) must be expected. We will keep record of number of days waiting for each person and include this as covariate in the analysis.
- **“Tankevirus” smartphone app:** The app will be downloaded to their personal smartphone, and the app will give push-notifications once new modules are released – every day for 3 weeks. The app has several procedures built in for engagement purposes but will not involve contact with a therapist. Usage data will be recorded to verify compliance. The app is developed in accordance with the requirements of the Norwegian Health Authorities and complies with data protection laws.

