For exploratory purposes, we will also examine predictors of relapse and predictors for the efficacy of these respective interventions for investigating whom that are most likely to benefit from these different options. In line with recent developments in clinical research, we will address outcome domains relevant from the adolescent perspective, like well-being and self-reported symptom load (37), described below.

SECONDARY OUTCOMES (between trial entry, at 3 months, 6 months, and 12-months):

Repetitive negative thinking - RNT-10 (38) assess transdiagnostic repetitive negative thinking, such as worry and rumination. The questionnaire will be translated into Norwegian by means of a back-translation procedure.

Somatic complaints – SSS8 is an 8-item questionnaire about somatic complaints, freely available and translated into Norwegian (39).

Well-Being - EPOCH Measure of Adolescent Well-Being(40) is a 20-item validated questionnaire that is freely available and will be translated into Norwegian by means of a back-translation procedure.

Health related Quality of Life - EQ-5D-5L + EQ VAS (41, 42) is available in Norwegian and will be used for economic evaluation of the interventions.

Use of health care services – adapted version of the Client Service receipt inventory (CSRI) will assess use of health services, medication use, and school absence.

ASSESSMENTS: Assessments at baseline will serve as predictors of outcome, and include age, gender, parental educational level as proxy for socioeconomical status, in addition to the assessments listed as secondary outcomes. Adolescents are required to fill in questionnaires repeatedly at 3, 6 and 12-month follow up. To maintain fidelity to the trial and prevent fatigue, we have prioritized short, validated scales. All assessments will be conducted within a digital environment (i.e., the research app). In addition to the primary and secondary outcome, at 3-month follow-up, the 8-item Client Satisfaction Questionnaire adapted to Internet-based interventions (CSQ-I (43)) will be administrated to those taking part in one of the two interventional arms.

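### RNT, the proposed mediator, is first re-measured at 3 months, so first relapses before then have no earlier post-baseline value; this weakens the mediation aim but does not defeat it

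*Protocol*

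**What the plan says.** Protocol section 1.1 sets an additional aim: "The project will also investigate the mediating effect of the hypothesized mechanism (i.e., RNT) on the subsequent relapse risk". Section 1.3 lists RNT-10 as the first of the secondary outcomes, all under one schedule: "SECONDARY OUTCOMES (between trial entry, at 3 months, 6 months, and 12-months". The ASSESSMENTS paragraph of the same section confirms it: "Adolescents are required to fill in questionnaires repeatedly at 3, 6 and 12-month follow up". No RNT score is planned between trial entry and month 3.

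Under INTERVENTIONS, the therapist-guided arm is delivered "in the form of 3 weekly 75-minutes sessions", and for that arm "a certain waiting period (~1 week) must be expected". In the app arm "the app will give push-notifications once new modules are released – every day for 3 weeks". Under PRIMARY ENDPOINT, relapse is followed for 12 months from randomisation, with a PHQ-4 prompt every two weeks.

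**The concern.** A mediator has to be measured after the intervention has acted and before the outcome it is meant to explain. Here the outcome is checked every two weeks, but the mediator is not seen again until month 3. A participant whose first relapse falls in that gap has only a baseline RNT score before it.

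Two analyses are then open for those participants, and both have a cost. A first-relapse landmark analysis at 3 months leaves them out and conditions on being relapse-free at the landmark, which treatment may itself influence. Using their 3-month score puts the mediator after the event, so a high score may be a result of the relapse. An analysis plan can choose between these, but it cannot supply a measurement that was never taken. The visit schedule is fixed in the protocol, so this is not a detail left to the SAP.

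**Working it through.** **Timing.** Three months is about 13 weeks.
- App arm: the programme ends at week 3, so the gap is 13 - 3 = 10 weeks.
- Group arm with a one-week wait: it ends at about week 4, so the gap is 13 - 4 = 9 weeks, or 8 weeks if the wait reaches two weeks.

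**Inputs from the protocol (STATISTICAL POWER).** Hazard ratio 0.6, 80% power, 0.05 level (taken as two-sided), 15% annual dropout, one year of follow-up, 165 per group. No relapse rate or hazard shape is given, so the 165 cannot be reproduced forwards. It can be used backwards to find the relapse rate it implies.

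**Step 1: events needed for two groups.**
- Schoenfeld: 4(1.96 + 0.84)² / (ln 0.6)² = 121.
- Freedman: (1.96 + 0.84)² × (1.6/0.4)² = 126.

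**Step 2: implied relapse rate.** With constant relapse hazard h and dropout hazard d = -ln 0.85 = 0.1625 per year, the expected proportion with an observed relapse by time t is h/(h + d) × (1 - exp(-(h + d)t)). Set 165 × [control proportion + treated proportion, treated hazard 0.6h] equal to the events at t = 1.
- 121 events: h = 0.637 in control; 12-month risks 47% (control) and 32% (treated).
- 126 events: h = 0.672; risks 49% and 33%.

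A log-rank simulation (4,000 runs per point) gave 79% power at a 45% control risk and 81% at 48%, which agrees.

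**Step 3: share of first relapses before month 3 in that scenario.** Apply the same formula at t = 0.25.
- 121 events: 38.6/121 = 32%.
- 126 events: 40.5/126 = 32%.

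**Step 4: sensitivity to what the protocol does not state.** Without dropout, share = (1 - exp(-0.25h)) / (1 - exp(-h)).

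| Assumption | Share before month 3 |
|---|---|
| Constant hazard, 12-month risk 10% to 70%, no dropout | 26% to 37% |
| Same, with 15% dropout | 28% to 39% |
| Front-loaded hazard (Weibull shape 0.7-0.8), risk 30-50% | 37% to 46% |
| Rising hazard (Weibull shape 1.2-1.5), risk 30-50% | 15% to 25% |
| All recurrent relapses counted at a constant rate | 25% |

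**Step 5: what an earlier score would change.** Constant hazard, no dropout, h = 0.38 to 0.67 (12-month risks 32% to 49%).

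| Time of first RNT score | h = 0.38 | h = 0.67 |
|---|---|---|
| Week 4 (end of group arm with a one-week wait) | 9% | 10% |
| Week 6 | 0.0429/0.316 = 14% | 0.0744/0.488 = 15% |
| Month 3 (as planned) | 0.0906/0.316 = 29% | 0.1542/0.488 = 32% |

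In the 121-event scenario with dropout, 18.6 events precede week 6 against 38.6 before month 3, so about 20 first relapses per pair of arms gain a preceding RNT score.

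**The case against.** **The aim concerns later risk.** Section 1.1 speaks of subsequent relapse risk, which a 3-month score can predict. Most first relapses come after it under every scenario tried. The primary endpoint also counts the number of relapses, so later relapses of early relapsers do follow an RNT score. This stands: a reader might infer that the mediation aim cannot be met, or that early relapsers must be discarded altogether, and the protocol supports neither. The loss is specific to analyses of first relapse, and the protocol does not fix a mediation model.

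**The share is not a protocol figure.** A reader might take about 30% as a fact about this trial. It is not: it depends on a relapse rate and a hazard shape that the protocol does not give. The range belongs with it.

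**Not all of the loss comes from the schedule.** About 9-10% of first relapses would precede even a score at week 4. This stands, and the net gain from a week-6 score is about half of the month-3 share.

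**The early months need not be special.** It is tempting to add that the missed period is when an effect is most likely. Nothing in the protocol says so, and its power simulation describes the effect by a single hazard ratio of 0.6 and fits proportional-hazards models. The point does not rely on it.

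**A light schedule is deliberate.** Section 1.3 favours short scales to prevent fatigue and names attrition as a risk. That is a fair reason to be sparing, but it weighs little against ten items asked once in an app that already prompts every two weeks.

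**Conclusion.** The gap is real and follows directly from the stated schedule: no post-baseline RNT value can precede a first relapse that occurs before month 3. Its size is conditional. Under constant hazard, 26-39% of first relapses are affected, about 32% at the relapse rate implied by 165 per group, and roughly 15-46% across the other hazard shapes tried. The mediation aim loses information on first relapse and, with a 3-month landmark, rests on a selected sample; it remains workable. The primary comparison and the sample size are unaffected, and nothing here is a miscalculation or a contradiction. This is an inexpensive improvement, between optional and a mild recommendation.

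**What to change.** Add RNT-10 once, in all three arms, at a scheduled biweekly PHQ-4 prompt shortly after the interventions end. Week 6 is a suitable example: it falls on a two-week grid counted from randomisation and, for a three-week programme, leaves room for a group-arm wait of up to about three weeks. Name it as the first post-intervention mediator measurement, and keep the scores at 3, 6 and 12 months.

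The cost is ten extra items on one occasion, a small burden in a trial that is concerned about attrition. It has to be decided before enrolment, because the score cannot be collected afterwards. If the schedule is kept as it is, the protocol should say that mediation of first relapse can be examined only for relapses after month 3.

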While clinical practice guidelines for adolescent depression treatment indicates that research on effective approaches to hinder relapse and recurrence are lacking and needs to be prioritized (17), meta-analytic evidence suggests that studies on relapse prevention in adolescence is scarce and of suboptimal quality and none have targeted relapse to anxiety (18). On a positive note, however, all strategies that have been employed (e.g., psychological interventions, pharmacological interventions, or a combination thereof), have demonstrated efficacy in either reducing relapse rates, or increasing the time until relapse.

In both anxiety and depression, repetitive negative thinking (RNT), like worry and rumination, is common, and is found to be a transdiagnostic factor partly explaining their co-occurrence both cross-sectionally and prospectively (19). RNT also plays an important role in somatic complaints, and fully mediate the relationship between vulnerability factors for both mental and physical disorders, such as the relation between neuroticism and pain (20) and stress and somatic complaints (21).

Interventions grounded in cognitive behavioral therapy can systematically reduce RNT, and thereby reduce relapse risk for depression and the tendency of anxiety to cross-over to depression. When negative thought content is recycled (i.e., rumination) or a tendency to anticipate negative scenarios are favored (i.e., worry), RNT introduces and sustains negative mood. Consequently, worry have been found to be a stronger predictor for depression relapse than residual depression (22) and rumination is known to predict relapse and recurrence of depression (23).

There is a pressing need for adopting new technology for serving the rising demand of mental health services (e.g., (24). By developing new methods that are scalable, we can reach more people in a

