STATISTICAL POWER: For the primary endpoint investigating number of relapses within the follow-up period, we will conduct a fixed effects omnibus ANOVA. Presuming Cohen's $f = .25$, alpha = .0167 (.05/3; Bonferroni corrected) and power = .8 including three groups, we will require a total sample size of 207 (GPower 3.1). Presuming 15 % dropout, we will need 238 adolescents to take part in the study. For time to relapse, the power analysis was performed using Monte Carlo simulation. A large pool of simulated survival data was generated, reflecting a hazard ratio of 0.6 between two groups, a 15% annual dropout rate with competing risk, and a 1-year observation period. The simulation titrated the sample size, drawing 10.000 random samples at each step and fitting Cox proportional hazards models. Power was estimated as the proportion of samples yielding statistically significant results at the 0.05 level. The analysis concluded that approximately 165 individuals per group, meaning that a total of 495 adolescents would be required to achieve 80% power for detecting a hazard ratio of 0.6 under the specified conditions. This simulation method accounts for the complexities of survival data, including censoring and limited observation time, providing a robust sample size estimate for the study design. All randomized participants will be subjected to analysis in accordance with an intention to-treat approach. The multiarmed parallel group randomized trial will be reported according to the extensions recommended by CONSORT (44).

RISK: Recruitment is the main risk factors of this trial. A few trials are currently under way in adolescent populations (e.g., StayFine trial (16), RuMeChange (15)) and in the first, they were in contact with 3018 adolescent during a three-year period. Their strict inclusion criteria and elaborate pre-inclusion assessments hindered several from participating, but still they had 589 eligible

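### Baseline RNT-10, which the protocol's own rationale treats as prognostic, is left out of the primary models it names; adjusting for it would gain some power at almost no cost

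*Protocol*

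**What the plan says.** Section 1.1 builds the rationale on repetitive negative thinking: "worry have been found to be a stronger predictor for depression relapse than residual depression (22) and rumination is known to predict relapse". Section 1.3 (Secondary outcomes) describes RNT-10 as the measure of worry and rumination. Its Assessments paragraph says of baseline data: "Assessments at baseline will serve as predictors of outcome, and include age, gender, parental educational level as proxy for socioeconomical status", and adds the scales listed as secondary outcomes, so RNT-10 is in the baseline set. The assessment-only arm completes all assessments too, so the value is taken in every arm.

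The Statistical power paragraph names the analysis for number of relapses: "we will conduct a fixed effects omnibus ANOVA". Time to relapse is sized by simulated Cox models with "a hazard ratio of 0.6 between two groups, a 15% annual dropout rate with competing risk, and a 1-year observation period". Neither mentions a baseline covariate.

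Two adjustment variables are fixed elsewhere in section 1.3. Days waiting is recorded for the therapist-guided arm, and the plan is to "include this as covariate in the analysis". The Ethics text says ongoing care will be controlled for in the outcome analysis. The study of relapse predictors is introduced as exploratory.

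**The concern.** A baseline variable that predicts the outcome explains part of its variation. Adjusting for it sharpens the comparison between arms without more participants. The protocol argues that worry and rumination predict relapse, pays the cost of measuring them before follow-up, and then names primary models that make no use of them. The two variables it does commit to have a weaker claim. Days waiting arises after allocation and is described for one arm only. Ongoing care is not limited to its value at entry, although new care may start during the trial.

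Power is at stake. Time to relapse is sized at 80% with no stated margin, and the protocol names recruitment as its main risk.

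**Working it through.** **Inputs from the protocol (section 1.3, Statistical power).** Count endpoint: Cohen's f = 0.25, "alpha = .0167 (.05/3; Bonferroni corrected) and power = .8 including three groups", and a stated N of 207. Time to relapse: hazard ratio 0.6, 15% annual dropout, one year, significance level 0.05, 165 per group.

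**Inputs that are assumptions.** The correlation r of baseline RNT-10 with the relapse count (0.1 to 0.5), the hazard ratio per SD of RNT-10 (1.2 to 2.0), and the 12-month control relapse risk. The protocol gives none of these.

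**Step 1. Reproduce 207.** One-way ANOVA, noncentral F with λ = N·f² and degrees of freedom 2 and N − 3. At N = 207, λ = 207 × 0.0625 = 12.94. The smallest N reaching 80% power is 205 at alpha 0.0167, which becomes 207 for three equal groups. Power at 207 is 0.805. The stated figure reproduces.

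**Step 2. Add one baseline covariate to the count analysis.** ANCOVA with λ = N·f²/(1 − r²) and degrees of freedom 2 and N − 4.

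| r (assumed) | λ at N = 207 | Power at 207 | N for 80% power |
|---|---|---|---|
| none (ANOVA) | 12.94 | 0.805 | 207 |
| 0.1 | 12.94/0.99 = 13.07 | 0.810 | 204 |
| 0.2 | 12.94/0.96 = 13.48 | 0.824 | 198 |
| 0.3 | 12.94/0.91 = 14.22 | 0.848 | 189 |
| 0.4 | 12.94/0.84 = 15.40 | 0.880 | 174 |
| 0.5 | 12.94/0.75 = 17.25 | 0.919 | 156 |

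**Step 3. Find a control risk that fits 165 per group.** Schoenfeld events for hazard ratio 0.6, two-sided 0.05, 80% power: 4 × (1.96 + 0.84)²/(ln 0.6)² = 121. Freedman gives 126. With 330 participants in a pair of arms, exponential times and 15% annual dropout as independent censoring, these event numbers imply a control relapse of 47% to 49% at 12 months. I take 48%. Simulated power without any covariate effect is then 0.80, in line with the plan.

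**Step 4. Cox models with and without the covariate.** 165 per arm, 4,000 simulated trials per row, RNT-10 standard normal, treatment hazard ratio 0.6 conditional on RNT-10, control risk held at 48%.

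| RNT-10 hazard ratio per SD (assumed) | Power unadjusted | Power adjusted | Estimated HR unadjusted | Estimated HR adjusted |
|---|---|---|---|---|
| 1.2 | 0.801 | 0.805 | 0.60 | 0.59 |
| 1.5 | 0.780 | 0.812 | 0.61 | 0.60 |
| 2.0 | 0.714 | 0.806 | 0.63 | 0.60 |

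The gain in this run is 0.4, 3.2 and 9.2 points. At an assumed control risk of 45% the gains are similar: 0.7 points (0.786 to 0.793), 2.7 points (0.741 to 0.768) and 9.3 points (0.691 to 0.784). Over the settings and runs tried, the gain at 2.0 per SD lies between about 7 and 10 points.

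**The case against.** The strongest reply is that covariate choice commonly belongs in the statistical analysis plan, which is not shown. The ANOVA is named beside its sample-size inputs, the Cox models appear only as a sizing device, and nothing forbids adding RNT-10. The sentence on baseline assessments as predictors could even be read loosely as naming covariates. That stands as far as it goes: a reader might infer that the protocol rules RNT-10 out, and it does not. But the protocol is not silent on adjustment. It names a model and fixes two adjustment variables, and RNT-10 is not one of them.

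A second reply is that the size is unknown. This stands too. A reader might infer from section 1.1 that RNT-10 is a strong predictor with complete data. The protocol gives no effect size, speaks of worry and rumination and not of the RNT-10 score, and does not say that baseline values will be complete. By its listed title, the source for worry concerns residual anxiety in bipolar II depression. By its title, the source for rumination is a review in adults. At the weak end of the range the gain is negligible.

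A third reply concerns the hazard ratio. A reader might take the unadjusted 0.63 against 0.60 as bias toward no effect. It is not: the marginal and the conditional hazard ratio are different quantities. The protocol's 0.6 is stated between two groups without a covariate and is most naturally the unadjusted ratio. On that reading planned power stays near 80% and adjustment only adds to it.

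Chance imbalance is a minor argument. With 165 per arm the SD of the between-arm difference in mean RNT-10 is √(2/165) = 0.11 SD. At 1.5 per SD that shifts the log hazard ratio by 0.11 × ln 1.5 = 0.045, or about 5%.

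**Conclusion.** The point holds as lost efficiency. The unadjusted randomised comparison remains valid, and the stated 207 is correct for its inputs. Nothing in the documents supports calling the named analysis biased or the sample size wrong.

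The benefit of adjusting runs from negligible to useful. For the relapse count it is about 2 points of power at r = 0.2 and 4 at r = 0.3. For time to relapse it is 0 to 1 point at a hazard ratio of 1.2 per SD, about 3 at 1.5, and 7 to 10 at 2.0. These figures rest on assumed associations, a control relapse near 48% inferred from the stated 165 per group, exponential times, dropout treated as independent censoring and, for the Cox results, a treatment effect of 0.6 conditional on RNT-10. The upper end is possible but has no support in the protocol.

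**What to change.** State in the analysis text that baseline RNT-10, as a continuous score completed before randomisation, is a prespecified covariate in both primary models: the ANCOVA or count model for number of relapses, and the Cox model for time to relapse. Add that the adjusted hazard ratio is conditional on baseline RNT-10, and say whether the 0.6 used for sizing is meant as conditional or marginal.

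The cost is one or two sentences. RNT-10 is already in the baseline set for all arms, so participants carry no added burden and the sample size need not change. The wording should be settled before outcome data are seen.
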